APPENDIX A.

BOHAN AND PETER CLASSIFICATION CRITERIA for Diagnosis of Dermatomyositis

Criterion	Definition
1. Symmetric weakness	Weakness of proximal limb-girdle muscles, progressing over weeks to months
2. Muscle Biopsy evidence	Evidence of necrosis of Type I and II fibers, phagocytosis, regeneration with basophilia, large vesicular sarcolemmal nuclei and prominent nucleoli, atrophy in a perifascicular distribution, variation in fiber size, and an inflammatory exudate, ofte perivascular
3. Elevation of Serum Muscle Enzymes level	Elevation in serum of any skeletal muscle enzyme, particularly creatine phosphokinase , aldolase, lactate dehydrogenase, aspartate aminotransferase and alanine amintransferase
4. EMG	Electromyographic triad of short, small, polyphasic motor units, Evidence fibrillations, positive sharp waves, and insertional irritability, and bizarre, high frequency repetitive discharges
5. Dermatologic Changes	A lilac discoloration of the eyelids (heliotrope rash) with periorbital edema (heliotrope rash), or a scaly, erythematous dermatitis over the dorsum of the hands, especially the metacarpophalangeal and proximal inter phalangeal joints, knees, elbows, and medial malleoli (Gottron's papules or sign)

^a Confidence limits can be defined as follows. For a definite diagnosis of dermatomyositis, three of four criteria plus the rash must be present. For a probable diagnosis of dermatomyositis, two criteria plus the rash must be present. Patients must be < 18 years of age at time of diagnosis to meet criteria for juvenile dermatomyositis.

The following findings exclude a diagnosis of dermatomyositis:

- Evidence of central or peripheral neurologic disease, including motor-neuron disorders with fasciculations or long-tract signs, sensory changes, decreased nerve conduction times, and fiber-type atrophy and grouping on muscle biopsy.

- Muscle weakness with a slowly progressive, unremitting course and a positive family history or calf enlargement to suggest muscular dystrophy
- Biopsy evidence of granulomatous myositis such as with sarcoidosis.
- Infection, including trichinosis, schistosomiasis, trypanosomiasis, staphylococcosis, and toxoplasmosis
- Recent use of various drugs and toxins, such as clofibrate and alcohol
- Rhabdomyolysis as manifested by gross myoglobinuria related to strenuous exercise, infections, crush injuries, occlusions of major limb arteries, prolonged coma or convulsions, high-voltage accidents, heat stroke, the malignant-hyperpyrexia syndrome, and envenomation by certain sea snakes.
- Metabolic disorders such as McArdle's syndrome.
- Endocrinopathies such as thyrotoxicosis, myxedema, hyperparathyroidism, hypoparathyroidism, diabetes mellitus, or Cushing's syndrome.
- Myasthenia gravis with response to cholinergics, sensitivity to d-tubocurarine, and decremental response to repetitive nerve stimulation.

Data from Bohan A. Peter JB. Polymyositis and dermatomyositis (first of two parts). N Engl J Med 1975;292:344-347,

APPENDIX B: Proposed New classification criteria for IIM *

Variable	Score	
	Without muscle biopsy data	With muscle biopsy data
18 ≤ Age of onset of first symptom assumed to be related to the disease < 40	1.3	1.5
Age of onset of first symptom assumed to be related to the disease ≥ 40	2.1	2.2
Muscle weakness		
Objective symmetric weakness, usually progressive, of the proximal upper extremities	0.7	0.7
Objective symmetric weakness, usually progressive, of the proximal lower extremities	0.8	0.5
Neck flexors are relatively weaker than neck extensors	1.9	1.6
In the legs proximal muscles are relatively weaker than distal muscles	0.9	1.2
Skin manifestations		
Heliotrope rash	3.1	3.2
Gottron's papules	2.1	2.7
Gottron's sign	3.3	3.7
Other clinical manifestations		
Dysphagia or esophageal dysmotility	0.7	0.6
Laboratory measurements		
Anti-Jo-1 (anti-Histidyl-tRNA synthetase) autoantibody positivity	3.9	3.8
Serum creatine kinase activity (CK) activity or Serum lactate dehydrogenase (LDH) activity or Serum aspartate aminotransferase (ASAT/AST/SGOT) activity or Serum alanine aminotransferase (ALAT/ALT/SGPT) activity	1.3	1.4
Muscle biopsy features		
Endomysial infiltration of mononuclear cells surrounding, but not invading, myofibers		1.7
Perimysial and/or perivascular infiltration of mononuclear cells		1.2
Perifascicular atrophy		1.9
Rimmed vacuoles		3.1

Risk score ≥ 5 (without biopsy) or ≥ 6 (with muscle biopsy) classified as myositis.

*A TjÄrnlund, M Bottai, LG Rider et al. The International Myositis Classification Criteria Project Progress Report on Development of Classification Criteria for Adult and Juvenile Idiopathic Inflammatory Myopathies. *Arthritis and Rheumatism*. 2012. 64(suppl). 23-324.

APPENDIX C : IMACS AND PRINTO CORE SET ACTIVITY MEASURES

IMACS Core Set Disease Activity Measures for Juvenile Dermatomyositis*

Core Set Variables	Core Set Measures
MD Global Activity	Physician global disease activity assessment by Likert or VAS
Patient/parent global activity	Parent/patient global disease activity assessment by Likert or VAS
Muscle strength	MMT(manual muscle test) by a 0-10 point or expanded 0-5 point scale to include proximal , distal, and axial muscles
Physical Function	Validated patient/parent questionnaire of activities of daily living (HAQ/CHAQ)
Laboratory Assessment	At least 1 serum muscle enzyme activity level from the following: CK, creatine kinase, aldolase, LDH, lactate dehydrogenase, AST, aspartate aminotransferase, ALT, alanine aminotransferase
Extra skeletal Muscle Disease Activity Assessment	MDAAT, Myositis Disease Activity Assessment Tool, extra muscular global activity assessment (constitutional, cutaneous, skeletal, gastrointestinal, pulmonary, cardiac) assessment score

*IMACS, International Myositis Assessment and Clinical Studies Group

PRINTO Core Set Disease Activity Measures for Juvenile Dermatomyositis *

Core Set Variables	Core Set Measures
MD Global Activity	Physician global disease activity assessment by Likert or VAS
Patient/parent assessment of overall well being	Parent/patient global disease activity assessment by Likert or VAS
Muscle strength	MMT(manual muscle test) by a 0-10 point or expanded 0-5 point scale to include proximal, distal, and axial muscles, or Validated observational tool of function, strength, and endurance, Childhood Myositis Assessment Scale (CMAS)
Physical Function	Validated patient/parent questionnaire of activities of daily living (HAQ/CHAQ)
Global Disease Activity	Disease Activity Score (DAS) or Myositis Disease Activity Assessment Tool (MDAAT)
Health Related Quality of Life	Childhood Health Questionnaire (CHQ) or SF-36 in adult patients

*PRINTO, Pediatric Rheumatology International Trials

APPENDIX D1.

IMACS definition of minimal clinical improvement, PRINTO definition of minimal, moderate, and major improvement and PRINTO criteria of inactive disease**

IMACS definition of minimal improvement	PRINTO definition of minimal improvement	PRINTO definition of moderate clinical improvement	PRINTO definition of major clinical improvement	PRINTO definition of inactive disease
≥ 20% of improvement in at least 3 of 6 core set measures, with ≤ 2 of the remaining worsening by > 25% (muscle strength cannot worsen)	≥ 20% of improvement in at least 3 of 6 core set measures, with ≤ 1 of the remaining worsening by ≥ 30% (muscle strength cannot worsen).	≥ 50% of improvement in at least 3 of 6 core set measures, with ≤ 1 of the remaining worsening by ≥ 30% (muscle strength cannot worsen).	≥ 70 of improvement in at least 3 of 6 core set measures, with ≤ 1 of the remaining worsening by ≥ 30% (muscle strength cannot worsen).	At least 3 of 4 criteria: CMAS ≥ 48; MD global Activity VAS ≤ 0.5 cm; CK ≤ 150; MMT ≥ 78.

*IMACS, International Myositis Assessment and Clinical Studies Group

**PRINTO, Pediatric Rheumatology International Trials

References:

**Rider LG, Giannini EH et al. International consensus on preliminary definitions of improvement in adult and juvenile myositis. International Myositis Assessment and Clinical Studies Group. Arthritis Rheum. 2004 Jul;50(7):2281-90. Review.

**Ruperto N, Pistorio A et al. The Paediatric Rheumatology International Trials Organisation provisional criteria for the evaluation of response to therapy in juvenile dermatomyositis. Arthritis Care Res (Hoboken). 2010 Nov;62(11):1533-41

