- 2) A health related quality of life measure, CHQ-PF50, is used and
- 3) Disease Activity Score (DAS) is used as a measure of global activity (42)

PRINTO also has a definition of minimal clinical improvement (20%), moderate (50%) and major (70%) improvement (41) (Appendix D).

PRINTO has also defined clinically inactive disease (41) as creatine kinase ≤ 150 (within normal limits), CMAS ≥ 48 , MMT ≥ 78 and Physician Global Activity VAS ≤ 0.2 . (41) (Appendix D)

The frequency of minimal, moderate and major improvement by the DOIs, with 20%, 50% and 70% change, as well as clinically inactive disease by the PRINTO criteria will also be examined in this trial.

Finally, the DOIs are currently undergoing revision in an ACR-EULAR project that is combining the efforts of IMACS and PRINTO. New definitions of minimal, moderate and major improvement have been developed and are expected to be finalized within the coming year. These newly-developed definitions will be added to the criteria as a secondary efficacy outcome measures for this trial (**Appendix D2**). Other criteria found to perform very highly in the ACR-EULAR project will be used as secondary endpoints in this trial (Appendix D2).

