	c. Has the patient had intolerance or an inadequate response to methotrexate at least 15 mg/week or 0.3 mg/kg or 15 mg/m ² / week for at least 3 months?
	d. Has the patient had intolerance or an inadequate response to mycophenolate mofetil at least 30 mg/kg/d or 1000 mg bid for at least 3 months?
	e. Has the patient had intolerance or an inadequate response to cyclophosphamide at least 1.0 mg/kg/d poor 500 mg/m ² /month IV for at least 3 months?
	f. Has the patient had intolerance or an inadequate response to oral tacrolimus for at least 3 months?
	g. Has the patient had intolerance or an inadequate response to cyclosporine at least 2.5 mg/kg/d for at least 3 months?
	h. Has the patient had intolerance or an inadequate response to IVIG at least 1.0 g/kg/month for at least 3 months?

	i. Has the patient had intolerance or an inadequate response to an anti-TNF agent (including Etanercept, Infliximab, Humira, etc) for at least 3 months?
	j. Has the patient had intolerance or an inadequate response to 2 infusions of Rituximab (375mg/m ² (for 4 doses), or 500 mg/m ² or 1000 mg for 2 doses)?
6	Considering 6a-6f, Does the patient have a moderately active disease (MD global VAS with a minimum value of 2,5 cm on a 10 cm scale plus another 2 other abnormal Core set Measures as listed above (7b-7f)
	a. Does the MD global VAS have a minimum value of 2.5 cm on a 10 cm scale
	b. Is the MMT-8 score no greater than 125/150
	c. Does the Patient/parent Global VAS have a minimum value of 2.0 cm on a 10 cm scale
	d. Does the CHAQ/HAQ disability index have minimum value of 0.25
	e. Is at least one of the muscles enzymes (including CK, aldolase, LDH, AST and ALT) elevated at a minimum level of 1.3 times the upper limit of normal. If more than one muscle enzyme is identified as being elevated and meeting the above guidelines, then the most abnormal will be selected and this enzyme will be the target enzyme followed to evaluate disease improvement or worsening.
	f. Does the Global extra-muscular disease have a score with a minimum value of 2 cm on a 10 cm VAS scale.
7	Is the prednisone dose stable for 4 weeks prior to the screening visit? (recommended dose ≤ 1.0 mg/kg/day)

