15.0 STATISTICS/DATA ANALYSIS

Statistical Plan:

This is an open label nonrandomized trial to assess the safety and efficacy of subcutaneous abatacept in 10 patients (children and adults) with juvenile onset refractory dermatomyositis (JDM).

We postulate that at least 6 of 10 patients with JDM will meet the myositis preliminary definition of improvement (DOI) after receiving 24 weeks of therapy with abatacept. Data will be entered and stored in the RedCap database, licensed to George Washington University. Primary analyses will be performed using intention to treat regardless of compliance with therapy or trial protocol. We will also perform analyses that include only those participants with known outcome data.

Summary statistics will be generated to describe the study samples. Descriptive statistics, including measures of central tendency (e.g. means, medians) and estimates of spread (e.g. standard deviations) will be used for continuous variables, including reporting of adverse event frequencies, core set measure assessments, and demographic and clinical variables. Non-parametric Wilcoxon signed rank tests will be used to investigate changes in continuous variables. 95% confidence intervals will be calculated for all point estimates.

We will examine the percentage of subjects meeting the DOI (20%), as well as moderate (DOI 50%) or major improvement criteria (DOI 70%), as well as frequency of patients achieving clinically inactive disease.

Due to the small number of subjects, it is unlikely that any statistical test would have the power to detect significant differences in any of the measured variables. We will therefore look not only at the percentage of subjects meeting improvement criteria by the DOIs, but also look for an improvement in individual core set myositis disease activity measurements of muscular and extra-muscular disease activity, as well as the in the patient-reported outcome measures, cutaneous assessments and MRI. We will also examine responsiveness after treatment using standardized response means and correlation degree of change between the measures. Differences between initial

and 24 weeks values will be analyzed by Student t distribution and Wilcoxon matched pair tests.

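### Under Appendix D1's 3-of-4 rule, though not under Section 2.1's wording, a patient who enters as moderately active can already be inactive at Visit 1, and Section 15 sets no Visit 1 condition on the count

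*Combined protocol and SAP*

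**What the plan says.** Three places have to be read together, and a fourth conflicts with one of them.

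- **Entry (Section 4.1, criterion 6).** Moderately active disease is "MD global VAS with a minimum value of 2,5 cm on a 10 cm scale plus another 2 other abnormal Core set Measures". The other measures are 6b ("Is the MMT-8 score no greater than 125/150"), 6c ("Does the Patient/parent Global VAS have a minimum value of 2.0 cm on a 10 cm scale"), 6d ("Does the CHAQ/HAQ disability index have minimum value of 0.25"), 6e ("Is at least one of the muscles enzymes (including CK, aldolase, LDH, AST and ALT) elevated at a minimum level of 1.3 times", taken against the laboratory's upper normal limit) and 6f, extra-muscular activity of at least 2 cm. Any two suffice.
- **Outcome (Appendix D1).** Inactive disease is "At least 3 of 4 criteria: CMAS ≥ 48; MD global Activity VAS ≤ 0.5 cm; CK ≤ 150; MMT ≥ 78".
- **Analysis (Section 15.0).** The plan reports the percentages meeting the improvement definitions, "as well as frequency of patients achieving clinically inactive disease". It states no condition on status at Visit 1.
- **Competing definition (Section 2.1).** The same outcome is worded as "creatine kinase ≤ 150 (within normal limits), CMAS ≥ 48 , MMT ≥ 78 and Physician Global Activity VAS ≤ 0.2", with no 3-of-4 rule, and the reader is then referred to Appendix D.

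**The concern.** The improvement definitions in Appendix D1 and the scores in Appendix D2 measure change from baseline, so a patient who does not change cannot meet them. Inactive disease is different: it is a state at one time point. Saying that a patient achieved it is justified only if the patient was not in that state before the first dose.

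Appendix D1 and the entry rule do not ensure this. If some patients are already inactive by D1 at Visit 1 and stay as they are, the planned frequency credits abatacept with an outcome that was present before treatment. The trial is single-arm and open-label, so no comparison group would reveal the baseline rate.

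**Working it through.** The plan states no figure to reproduce. The check is whether the two definitions can hold in the same patient.

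**Step 1: each D1 item against the entry rule.**

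| D1 item | What entry requires | Failure guaranteed at entry? |
|---|---|---|
| Physician global ≤ 0.5 cm | ≥ 2.5 cm, mandatory (6a) | Yes |
| CMAS ≥ 48 | Nothing | No |
| CK ≤ 150 | 6e is optional and can be met by aldolase, LDH, AST or ALT | No |
| MMT ≥ 78 | 6b is optional | No |

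One item must fail and D1 tolerates one failure, so the definitions are compatible.

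**Step 2: a worked patient.** Physician global 5, patient global 4, extra-muscular VAS 5, full MMT-8, CMAS 52, CK 100.

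- Entry: 6a, 6c and 6f are met, so the patient has moderately active disease.
- D1: CMAS, CK and MMT are met and physician global is not. That is 3 of 4, so inactive.
- Section 2.1: physician global 5 exceeds 0.2 and all four items are joined, so not inactive.

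Nothing else in Section 4 necessarily excludes this patient. Criterion 1 asks for documented weakness or enzyme elevation, which may lie in the past.

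**Step 3: how many entry routes leave room.** Combinations of at least two of 6b–6f: 10 + 10 + 5 + 1 = 26. Without 6b: 6 + 4 + 1 = 11. Without 6b and 6e: 3 + 1 = 4.

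The 11 depends on the scale of the MMT cut-off, which D1 does not give. Section 14.0 allows 0–80 (8 × 10) or 0–150 (7 × 2 × 10 + 10).

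- 78 read on 0–80: 78/80 = 97.5% of maximum, about 146/150 by proportional scaling. The 6b limit, 125/150, scales to about 66.7/80, so routes using 6b are treated as incompatible. 11 of 26 combinations remain, or 6 of the 10 minimal pairs.
- 78 read on 0–150: 78/150 = 52% of maximum. A score between 78 and 125 meets both 6b and the D1 item, so all 10 pairs, and hence all 26 combinations, are compatible.

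Under Section 2.1, or under D1 with the physician-global item made mandatory, 0 of 10 pairs are compatible while physician global stays at 2.5 cm or more.

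**Step 4: size.** With n = 10, each unchanged, already inactive patient adds 1/10 = 10 percentage points. One such patient alone gives 10% (95% CI 0.3% to 44.5%); two give 20% (2.5% to 55.6%).

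The share q of entrants inactive by D1 at Visit 1 is not in the documents. As an assumption, P(at least one of 10) = 1 − (1 − q)^10:

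| q | 5% | 10% | 20% | 30% |
|---|---|---|---|---|
| P(at least one) | 40% | 65% | 89% | 97% |

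Illustration: one new case plus two unchanged patients already inactive is reported as 3/10 = 30%. Among those not inactive at Visit 1 it is 1/8 = 12.5%.

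**The case against.** The strongest reply is that the defect exists under only one of the protocol's two definitions. If Section 2.1 governs, no patient whose physician global is still at the entry level can be inactive. That is correct, and it makes the point conditional. It does not dispose of it, because Section 2.1 sends the reader to Appendix D, where the rule is 3 of 4. Aligning only the physician-global cut-off (0.2 against 0.5) and keeping 3 of 4 would leave the overlap in place.

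The second reply is about weight. Inactive disease is not among the endpoints in Section 3.1 or the synopsis objectives; it is a frequency to be examined, with no target. That stands. A reader might infer that the main efficacy result is compromised. It is not: the primary definition of improvement requires change from baseline.

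Third, a reader might take 11 of 26 as the proportion of patients affected. The documents do not support that. The count shows which routes are possible, not how often they are taken, and not using 6b or 6e does not mean that D1 is met. On the 0–80 reading, an MMT-8 of 126 to 145 out of 150 fails both 6b and the D1 item; CK may exceed 150 without reaching 1.3 times the laboratory's limit; and CMAS must be at least 48 as well.

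Fourth, simply excluding patients already inactive at Visit 1 from the numerator would create the opposite error. If the worked patient's physician global fell to 0 and the skin disease cleared, that genuine responder could never count, yet would remain in a denominator of 10. This is right and shapes the fix.

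Finally, the components are collected at both visits and 'achieving' ordinarily implies a new state, so a careful analyst might notice the overlap. The plan still does not say what to do about it.

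**Conclusion.** The point holds in conditional form. Under Appendix D1, though not under Section 2.1, an eligible patient can be inactive at Visit 1, and Section 15 would let that patient count as having achieved inactive disease without any change. Each such patient is worth 10 percentage points at n = 10.

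This rests on three assumptions: D1's 3-of-4 rule is the one applied; the relevant values are unchanged between screening and Visit 1, which may be up to 45 days apart; and the count is taken at week 24 over all 10 patients.

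It does not follow that the reported rate will be inflated, or by how much, because the share of affected entrants is not given. The matter concerns one descriptive outcome. It deserves correction because an uncontrolled trial has no other safeguard against this misreading.

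**What to change.** 1. Reconcile Section 2.1 and Appendix D1 into one definition (all four items or 3 of 4, and one physician-global cut-off), and state the MMT scale to which 78 refers.
2. If a 3-of-4 rule is kept, add to Section 15 a Visit 1 by week 24 cross-table of inactive-disease status. Count new inactive disease only among patients not inactive at Visit 1, with their number as the denominator, and state how many already met the definition.
3. Alongside it, report for all 10 patients the week-24 count with the physician-global item required. A patient with normal strength and CK at entry whose disease truly clears is then still credited.

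The cost is a few sentences and one small table. CMAS, MMT-8, CK and physician global are already scheduled at weeks 0 and 24 (Section 7.1 and Appendix E). The number of new cases can only stay the same or fall, and the denominator may be below 10.

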Appendix D2. Newly Developed Criteria for Myositis Clinical Response (pending ACR-EULAR approval).

Definition 20: 1000 Minds Model 3 (absolute % change)	
Core Set Measure	Improvement score for each level
MD Global Absolute % Change	
Up to <=5%	0
>5% up to <=15%	7.5
>15% up to <=25%	15
>25% up to <=40%	17.5
>40%	20
Pt Global/Par Global Absolute % Change	
Up to <=5%	0
>5% up to <=15%	2.5
>15% up to <=25%	5
>25% up to <=40%	7.5
>40%	10
MMT/CMAS Absolute % Change	
Up to <=2%	0
>2% up to <=10%	10
>10% up to <=20%	20
>20% up to <=30%	27.5
>30%	32.5
HAQ/CHAQ Absolute % Change	
Up to <=5%	0
>5% up to <=15%	5
>15% up to <=25%	7.5
>25% up to <=40%	7.5
>40%	10
Enzyme/CHQ-PF50 Absolute % Change	
Up to <=5%	0
>5% up to <=15%	2.5
>15% up to <=25%	5
>25% up to <=40%	7.5
>40%	7.5
ExtraMusc/DAS Absolute % Change	
Up to <=5%	0
>5% up to <=15%	7.5
>15% up to <=25%	12.5
>25% up to <=40%	15
>40%	20

Improvement Score (sum of all CSM)		
Profile	Improvement Category	Cutpoint
Adult	Minimal	20
	Moderate	40
	Major	60
Pediatric (IMACS/PRINTO)	Minimal	30
	Moderate	45
	Major	70

APPENDIX E TABLE 1 AND TABLE 2 /2a: STUDY SCHEDULE OF EVENTS

Table 1.

Study Events	Treatment Week														
	Screening	W0	W2	W4	W6	W8	W10	W12	W14	W16	W18	W20	W22	W24	W25-W48
Visit	V1				V2			V3			V4			V5	V6 (extension)
Phone f/up*			X	X		X	X		X	X		X	X		
Informed Consent/Assent	X														
Inclusion/Exclusion Criteria	X														
Vital signs, Weight, (pulse oximetry) is changed to screening evaluation	X	X			X			X			X			X	X
Brief physical evaluation		X			X			X			X			X	X
CMAS	X	X			X			X			X			X	X
MMT8	X	X			X			X			X			X	X
MDAAT (EM Global only at Screening)	X	X			X			X			X			X	X
Disease Activity Score		X			X			X			X			X	X
MD Global Activity (VAS)	X	X			X			X			X			X	X
Patient/Parent Global Activity (VAS)	X	X			X			X			X			X	X
CHAQ/HAQ	X	X			X			X			X			X	X
CHQ-PF50/SF36		X			X			X			X			X	
Myositis Damage Index		X												X	
Urine Pregnancy , UA,	X	X			X			X			X			X	X
Screening Blood Tests	X														
Research Blood Tests form is changed to blood sample tracking form (regular and research blood test)		X						X						X	
Chest X-ray	X														
Plain radiograph for calcinosis (calcinosis pts only)		X												X	
Muscle MRI (bilateral, Axial and T1)		X												X	
MD Global Disease Damage (VAS)		X			X			X			X			X	X
Physician Assessment of Study Outcome					X			X			X			X	X

Dermatology assessment ([name] Global Skin Activity/Damage performed by Dermatologist) Optional		X						X						X	
CDASI (performed by Rheumatologist)		X			X			X			X			X	X
DLQI, skin itch, Patient and MD skin global activity/damage (performed by Rheumatologist)		X			X			X			X			X	X
Photograph Documentation (if applicable)		X			X			X			X			X	X
Nailfold capillaries photograph (Optional)		X						X						X	X
PROMIS and PedsQL fatigue		X			X			X			X			X	X
Review medication log and self-administration log		X			X			X			X			X	X
NCI CTC Assessment		X			X			X			X			X	X
Adverse Events assessments		X	X	X	X	X	X	X	X	X	X	X	X	X	X
Prednisone taper if meet DOI and rated at least minimally improved					X			X			X			X	X
Increase Abatacept dose if ≤ 5% improved by DOI and rated as unchanged or worsened								X							
Administer Abatacept medication		X			X			X			X			X	X
Visit		V1			V2			V3			V4			V5	V6
Week	Screening	W0	W2	W4	W6	W8	W10	W12	W14	W16	W18	W20	W22	W24	W25-W48

*Phone f/up at W2, 4, 8, 10, 14, 16, 20, and 22 will consist of evaluation of Adverse Events.

Abbreviations: CMAS, Childhood Myositis Assessment Scale; MMT8, manual muscle testing 8 muscle groups; MDAAT, Myositis Disease Activity Assessment Tool; EM Global, Extra muscular Global; CHAQ/HAQ, Childhood Health Assessment Questionnaire/Health Assessment Questionnaire; CHQ-PF50, Childhood Health Questionnaire, parent form 50; SF36, Short Form 36; CDASI, Cutaneous Dermatomyositis Assessment and Severity Index; DLQI, Dermatology Life Quality Index

Table 2 (*)

Test	Collection Date	Collection Tube	Matrix	Required volume (ml) for	
				Children	Adults
Comprehensive Metabolic Panel (Chem 14)	Screen, W0, 6,12,18,24, 25-48	Gold SST top tube	Serum	2.5	4.0
Complete blood count (CBC) with diff	Screen, W0, 6,12,18,24, 25-48	Lavender top tube	Whole Blood	1.5	3.0
Von Willebrand Factor Antigen	W0,6,12,18,24	Blue top tube	Plasma	1.0	1.0
Thyroid function test, TSH, Thyroid Abs	W0, 24	Red top tube	Serum	4.0	4.0
Glutamyl Transferase (GGT)	Screen, W0,6,12,18,24, 25-48	Green or Red top tube	Serum	0.6	0.6
Creatine Kinase (CK)	Screen, W0,6,12,18,24, 25-48	Gold SST tube/Red top	Serum	5.0	5.0
Aldolase	Screen, W0,6,12,18,24, 25-48	Red top tube	Serum	3.0	3.0
Lactate Dehydrogenase (LDH)	Screen, W0,6,12,18,24, 25-48	Red top tube	Serum	1.0	1.0
HIV Ab	Screen	Lavender top tube	Serum	2.0	2.0
Hepatitis panel (HBsAg, Anti-HBc, Anti-HepC) ,CD19 (for those who received rituximab before)	Screen	Red /black SST tube	Serum	8.0	12.0
Quantiferon-gold TB test	Screen	Test Special kit	Whole blood	3.0	3.0
Lymphocyte Phenotyping-TBnk/Flow cytometry	W0,12,24	Lavender top tube	Whole blood	2.0	2.0
Antinuclear Abs (ANA) and ENA (extractable nuclear Abs) comprehensive panel	W0,24	Red (stopper) tube	Serum	2.0	2.0
PK, immunogenicity	W0.12.24			10.0	10.0
Quantitative Immunoglobulins G and M	W0	Red top tube	Serum	2.0	2.0
Myositis-Specific and Myositis-Associated Ab (MSA and MAA) test	W0	Red (stopper) tube	Serum	5.0	5.0
Research Immunology Tests at Ross Hall:	W0,12,24	Heparinized tube	Whole blood	60.0	60.0
1. FACS Immunophenotyping for CD4, CXCR3, IFN γ (TH1), CD4, CCR4, CRTH2, IL4(TH2), CD4, CCR6, IL17 α (TH17), CD4, CD25, Foxp3 (T regulatory cells), B cell markers, macrophage markers along with B71, B72, CTLA4, CT28					
2. Cytokine Human Magnetic 30-Plex Panel					
3. RNA isolation and RNA Quality Check					
4. Illumina Human Gene Bead Chip Panel					

5. Illumina Data Analysis and Ingenuity Pathways Analysis					
Urinalysis	Screen, W0,6,12,18,24,25-48	Urine cap	Urine	1.0	1.0
Urine pregnancy Test	Screen, W0,6,12,18,24,25-48	Urine cap	Urine	1.0	1.0

(*) NIH guidelines for limits of blood drawn for research purposes will be followed:

Adult Patients and Volunteers: Blood Drawing Limits for Research Purposes

The amount of blood that may be drawn from adult patients and volunteers (i.e., those persons 18 years of age or older) for research purposes shall not exceed 10.5 mL/kg or 550 mL, whichever is smaller, over any eight week period. The amount of blood to be drawn from volunteers and the frequency of collection shall be specified in the clinical research protocol, and exceptions to the 10.5 mL/kg or 550 mL limitations shall be approved by the IRB.

Pediatric Patients: Blood Drawing Limits for Research Purposes

For pediatric patients, no more than 5 mL/kg may be drawn for research purposes in a single day, and no more than 9.5 mL/kg may be drawn over any eight-week period.

Table 2a : Summary of blood collection

	Blood Volume (ml)	
	Children	Adult
Screen	28.6	35.6
W0	105.7	114.2
W6	14.6	17.7
W12	86.6	89.6
W18	14.6	17.7
W24	92.6	95.6
W 25-48	13.5	16.6

